## 2.2 SPECIFIC AIMS: Sleep-Disordered Breathing and CPAP after Adenotonsillectomy in Children

Obstructive sleep-disordered breathing (SDB) affects at least 2-3% of children and may have substantial adverse impact on behavior and cognition. Adenotonsillectomy (AT), the second most common surgical procedure in children, is now performed more often for suspected SDB than for any other indication. However, recent studies among an increasingly obese population now show something alarming: many if not most children still have SDB after AT, and many still suffer from residual neurobehavioral morbidity. Furthermore, the investigators' ongoing, 12-year, NIH-funded research has shown that standard preoperative polysomnographic measures of SDB do not consistently predict post-AT improvement in behavior and cognition. This may arise in part because many children after AT still have SDB, and because linear relationships between standard SDB measures and neurobehavioral morbidity may not exist. Even at subtle levels, SDB may promote significant neurobehavioral morbidity. Some have suggested that polysomnography may be more important after AT than before AT. However, in practice few children receive polysomnography before AT, and even fewer after AT, when continuous positive airway pressure (CPAP) could still provide definitive relief from SDB. Preliminary data from our group suggest that CPAP after AT is well-tolerated by most children and may provide significant benefit. However, virtually no published evidence exists to address critical clinical questions: which children benefit most from CPAP after AT; what role can clinical symptoms or polysomnography play in that determination; and what neurobehavioral gains are achieved by CPAP after AT?

The investigators therefore propose a highly practical, clinical study with **two main goals: (1) to assess the extent that behavior, cognition, and sleepiness in children can improve with CPAP after AT, and (2) to identify which patients stand to gain most from post-operative assessment and treatment.** This research will use reversible SDB-related neurobehavioral morbidity as the criteria by which to judge the utility of clinical symptoms and polysomnography in identification of candidates for CPAP after AT. Neurobehavioral outcomes will be assessed with instruments shown to be sensitive to SDB in the past. Clinical sleep symptoms will be assessed by use of a pediatric SDB questionnaire developed and validated by the investigators and now used around the world. Standard polysomnography will be supplemented by innovative approaches shown by the investigators to help identify subtle pediatric SDB. Subjects will be 5-12 years old and have had AT in recent months for suspected SDB. To enroll a reasonable distribution of children with and without obvious SDB symptoms after AT, the sample will be enriched selectively if necessary. *All analyses will be adjusted for body mass index z-scores.* These novel investigations will come at a critical juncture and could well transform clinical care for an exceedingly common and consequential childhood condition.

**Aim 1:** Complete parental sleep questionnaires, sleep laboratory-based nocturnal polysomnograms, Multiple Sleep Latency Tests of daytime sleepiness, parental behavioral ratings, and neuropsychological tests for  $n=120$  children 4 months after AT for clinically suspected or laboratory-confirmed SDB.

**H1a:** After AT, an SDB symptom scale will help identify children who have residual SDB on polysomnography.

**H1b:** After AT, residual problems with behavior, cognition, and sleepiness will show associations with persistent SDB as identified by the SDB scale or polysomnography.

**Impact:** Results will show that after AT, a symptom-based questionnaire can help identify children likely to have residual SDB, which in turn is a risk factor for persistent neurobehavioral morbidity. Clinicians and families will have, for the first time, data that can guide evaluation after an exceedingly common surgery.

**Aim 2:** *Randomize Aim 1 subjects to receive 6 months of standard clinical care (control group,  $n=40$ ) vs. CPAP titration (CPAP group,  $n=80$ ), home use of CPAP, and monitored adherence; and then re-assess all subjects with all baseline sleep and neurobehavioral tests.*

**H2a:** Among CPAP subjects who have adhered to the therapy, residual questionnaire or polysomnographic evidence of SDB from 4 months post-AT, as compared to no residual SDB, will predict greater improvement 10 months post-AT in hyperactive behavior, attention deficit, and sleepiness.

**H2b:** Among all CPAP subjects ( $n=80$ ), neurobehavioral outcomes will improve more, from baseline to follow-up, among subjects who adhere successfully to CPAP than among those who do not.

**H2c:** *Among all subjects ( $n=120$ ), neurobehavioral outcomes will improve more among CPAP subjects than control subjects in an intent-to-treat analysis.*

**Impact:** Results will demonstrate the clinical utility of an SDB questionnaire and polysomnography after AT; implicate post-AT residual SDB as a potential cause of persistent neurobehavioral problems; and suggest that successful treatment of post-AT SDB provides tangible clinical benefits.

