One week prior to each sleep study, an investigator will call the family to confirm the appointment, verify absence of unexpected illness, and encourage completion of a one-week sleep log. Nocturnal sleep studies will be performed by registered, child-experienced sleep technologists in the 10-bed Michael S. Aldrich Sleep Disorders Laboratory, where 4 spacious rooms specifically designed to accommodate young children, and parents in a separate bed, are available also for research use. *Weight and height will be measured at the laboratory.* The next day, a Multiple Sleep Latency Test will be administered. Between naps, a trained technician will administer neuropsychological tests. All children will be tested after a night in the same environment, equivalent opportunities for good sleep, and measured total sleep times. During each child's testing, a parent will complete behavioral rating scales, the Pediatric Sleep Questionnaire (described above), and a standard measure of socioeconomic status. After the sleep studies at 4 months post-AT, submission of electronic adherence data (CPAP group) or other follow-up information (control group) at 7 months, and final assessments at 10 months, each child will receive a \$30 gift certificate. After evaluations at 4 months and 10 months post-AT, each parent will receive \$250 for their time spent on this research. Parents will also be compensated for timely, monthly follow-up contacts (\$5 for each contact completed within 5

business days of the target follow-up call date), which are important in assessing possible safety concerns on study.

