An unmasked, board-certified sleep specialist will interpret each sleep study, not to provide study variables but rather to inform families and their physicians. Study results generally will not be communicated until after the participant has finished the entire protocol, when sleep and psychological test results are fully scored. However, an investigator will promptly communicate any finding that could have medically urgent significance for the patient, such as an unsuspected arrhythmia, paroxysmal EEG spikes, or severe residual SDB.

Nocturnal polysomnograms and Multiple Sleep Latency Tests will be scored by a single chief technologist ([name], RPSGT, REEGT) masked to subject identity. This technologist has meticulously scored about 1,000 pediatric sleep research studies in the past 10 years. Borderline polysomnographic features will be arbitrated between the technician and the PI. Scoring will be performed in batches: pre- and post-PAP studies of 5 subjects will be randomly ordered and presented for scoring. This procedure, used for two past R01s, assures that any subtle changes in scoring tendencies over time do not confound pre- vs. post-PAP comparisons. Scoring for sleep stages, respiratory events, periodic leg movements, and arousals will follow standard criteria for children. Double-scoring of arousals and respiratory events, in 20% of the records, will be performed to generate a Kappa statistic for intra-rater reliability. Inter-rater reliability will also be determined by having another experienced polysomnographic technologist score these same records.

For Multiple Sleep Latency Tests, the sleep latency of each nap will be scored as the time between lights out and the first epoch of stage 1 sleep. The mean sleep latency across naps is the most well-validated and commonly used objective measure of daytime sleepiness in both adults and children. Childhood sleepiness as a continuous variable for research purposes can be detected in SDB patients as young as 3 years old by questionnaires and by Multiple Sleep Latency Tests.

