**C10.2.** The pediatric SDB questionnaire to be used in this study was developed and validated by the investigators, and shown to be useful in many research studies. The 22-item SDB component of the Pediatric Sleep Questionnaire asks about chronic snoring, snorting, observed apneas, other breathing difficulties, ancillary symptoms, and behavioral signs (see appendix), each of which individually predicts childhood SDB as confirmed by polysomnography. The scale can be licensed online from the University of Michigan by any investigator at no cost. When tested against polysomnographically-defined pediatric SDB, the SDB scale showed a sensitivity of 0.81, specificity of 0.87, and overall classification accuracy of 85%, with good internal consistency and test-retest reliability. In a subsequent study of 78 children who underwent AT for clinical purposes, and 27 controls, the SDB scale identified subjects with polysomnographically-confirmed SDB both before and one year after AT. The SDB scale predicted current hyperactive behavior, sleepiness (mean sleep latency), and their responses to AT at least as well as sleep studies did. However, these important findings require confirmation, as the original aims of the research did not include these analyses. Furthermore, no data were collected on response to PAP. Nonetheless, the SDB scale is now used in many studies at the University of Michigan, elsewhere in the U.S., and around the world, where it has been translated (at minimum) into Spanish, German, Chinese, and Turkish, with Korean and Portuguese versions in progress.

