**6.2.b Protection Against Risk:** Fatigue and anxiety during cognitive testing will be minimized by a neuropsychology technician who has extensive experience with children and will give breaks from testing as needed. If results of behavioral or cognitive assessments engender parental concern, the child and parents will be invited back to a meeting with a child psychologist co-investigator, who will discuss the findings in an appropriate manner and review options for further evaluation or treatment outside the research protocol. Prior to study enrollment, tours of the sleep laboratory will give subjects and families a preview of that environment and equipment used there, reduce any possible fears or anxieties, and give them a good understanding of study requirements in relation to family, school, and job commitments. Technicians experienced with children and anxieties of this age group will conduct sleep studies. Children will be offered a topical anesthetic prior to insertion of the esophageal pressure catheter. However, children who do not tolerate placement of the esophageal catheter (anticipated based on this group's past work to constitute a minority of these volunteer subjects) or other equipment will not be required to use them. Parents will stay with children during overnight testing to reduce separation anxiety. Spacious pediatric sleep rooms are designed to include a separate bed for the parent. We will instruct subjects who obtain poor sleep in the laboratory to avoid operating dangerous toys, bicycles, and machinery until adequate sleep is recovered. We will also ask parents to supervise such children at home until restorative sleep is obtained. During sleep studies, a physician investigator will always be on call for any unexpected emergencies. Studies will be performed at the Sleep Disorders Center in the 10-bed Michael S. Aldrich Sleep Disorders Laboratory, where a 24-hour technical staff including pediatric and research technologist pods is well prepared to meet the needs of children and families who participate in research. If a cutaneous reaction to electrode placement occurs, technicians will remove the electrode and reapply it at another site with a different type of adhesive. Mild skin irritation will be treated with topical creams as needed. Moderate reactions at multiple sites, or any severe reaction, will warrant study termination. Finally, every effort will be made to ensure, as in the investigators' past NIH-funded pediatric sleep protocols, that this research experience is fun, positive, and rewarding for each subject and family.

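### The 4-month sleep questionnaire is completed the day after the parent stays in the child's room for the polysomnogram, so the H1a index test may be influenced by the reference-test night

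*Combined protocol and SAP*

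**What the plan says.** H1a, in the Specific Aims, is that "After AT, an SDB symptom scale will help identify children who have residual SDB on polysomnography". C8 makes the 22-item scale score the main explanatory variable and RDI of at least 1 the outcome, in a logistic regression.

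C3 gives the order of the 4-month visit. The nocturnal study comes first. Then: "The next day, a Multiple Sleep Latency Test will be administered", with neuropsychological tests between naps. During that testing "a parent will complete behavioral rating scales, the Pediatric Sleep Questionnaire" and a socioeconomic measure.

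Section 6.2.b (Protection Against Risk) says: "Parents will stay with children during overnight testing to reduce separation anxiety", and "Spacious pediatric sleep rooms are designed to include a separate bed for the parent". C3 describes the rooms in the same way.

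On what the parent learns, C4 says: "Study results generally will not be communicated until after the participant has finished the entire protocol", except for medically urgent findings. On content, C10.2 says that the scale "asks about chronic snoring, snorting, observed apneas, other breathing difficulties, ancillary symptoms, and behavioral signs".

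**The concern.** H1a is in effect a diagnostic-accuracy question. The questionnaire is the index test and the polysomnogram is the reference. The intended use, under Aim 1's impact statement, is to guide evaluation after surgery, where the plan itself says few children have a polysomnogram. A parent in that setting answers without having just spent a night in a room with the child.

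In the trial as described, the parent has. Snoring, snorting and pauses are things a parent in the room may see or hear, and the scale asks about them. If that night moves some answers, questionnaire and RDI share a source of information that they would not share in practice, and the likely direction is towards agreement. C8's secondary H1a analyses of the snoring subscale and the single habitual-snoring item would be the most exposed.

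C8 already guards against one artificial correlation: for H1b it drops the behavioral items because they overlap with the outcome. H1a has no comparable safeguard for the order of the two tests. Without completion times, the problem could be neither detected nor corrected afterwards.

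**Working it through.** **1. Order of events at the 4-month visit.**
- Night: polysomnogram, with the parent in the child's room (C3; 6.2.b).
- Next day: sleep latency test, cognitive tests, and the parent's questionnaire during that testing (C3).
- Scored result: generally held back until the family has finished the protocol (C4; 6.2.b).

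**2. Whether another section changes that order.**
- C2's enrichment rule uses a 4-month score obtained before randomization, which does not place it before the sleep study.
- Section 6.1.a describes questionnaires before surgery, but H1a concerns the post-surgery score.
- C5 allows paper, email or web forms, which permits earlier completion but does not require it.
- No section sets a recall period that excludes the laboratory night or asks for a completion time.

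The two tests are therefore not collected independently as the plan is written.

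**3. The plan's own figure.** C9 gives 80% power for a Spearman correlation of 0.25 at alpha .05. Aim 1 gives n = 120. Sidedness is not stated; two-sided is assumed.

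Power = Φ(atanh(0.25) × √(120 − 3) − 1.960) = Φ(0.2554 × 10.817 − 1.960) = Φ(0.803) = 78.9%.

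This reproduces the stated 80% to within rounding. The sample size is not in question.

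**4. Illustration only.** The documents give no figure for carry-over. Suppose that observed score = uncontaminated score + w × polysomnographic severity, both standardized, where w is an assumption that starts at zero. Then

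r(observed) = (r + w) / √(1 + 2wr + w²).

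The chance of a significant positive result is from the formula in step 3.

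| w | true r = 0: observed r | chance | true r = 0.15: observed r | chance |
|---|---|---|---|---|
| 0 | 0.00 | 2.5% | 0.15 | 37% |
| 0.05 | 0.05 | 8% | 0.20 | 59% |
| 0.10 | 0.10 | 19% | 0.25 | 77% |
| 0.20 | 0.20 | 58% | 0.33 | 96% |

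Worked example: r = 0.15 and w = 0.10 give 0.25 / √1.04 = 0.245.

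The table leans high for two reasons. It lets the parent's impression track measured severity without error. It also uses severity as a continuous quantity, whereas H1a's main test uses RDI of at least 1. If 66% of children are positive (89 of 135 in C10.3, there with RDI above 1), and assuming normality, dichotomizing multiplies a correlation by 0.366 / √(0.66 × 0.34) = 0.77. An observed 0.20 becomes about 0.15, and 0.33 becomes about 0.26. The table shows that modest carry-over would matter if present. It does not show that there is any.

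**The case against.** The strongest case on the other side is that the route for carry-over is narrow.
- The parent does not see the scored polysomnogram, apart from urgent findings, and scoring is masked to subject identity (C4).
- The parent may be asleep for much of the night.
- The scale asks about chronic symptoms, includes ancillary and behavioral items, and is reported to have good test-retest reliability (C10.2). One night competes with about four months of observation at home.
- RDI counts hypopneas and effort-related arousals, which need instruments to detect, and section A3 says that residual disease after surgery is usually not severe.
- Operational detail is left to manuals that are not part of these documents, so next-day completion is described rather than strictly fixed.

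All of this stands as reason to expect a small effect, possibly none. It does not remove the gap. Withholding the result does not stop a parent from noticing the night, and permission to use email or web forms does not set an order.

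A reader might infer that the score is already informed by the reference test and that H1a does overstate performance. The documents do not support that: they establish the sequence, not that any answer changes. A reader might also extend the bias to H1b and H2a. Those hypotheses have neurobehavioral outcomes, with the questionnaire or RDI as the explanatory variable, and neither test needs the two to be independent. The documents show no mechanism for bias there.

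**Conclusion.** The point holds as a design weakness in H1a. As described, the index test is collected after the parent has shared the reference-test night, and nothing keeps the two apart. Upward bias in the apparent value of the scale is the plausible direction. Neither its presence nor its size can be established from the documents, and zero is possible. The table under the check is conditional on an assumed w and should not be read as an estimate.

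The conclusion rests on C3 describing the intended order and on the unseen manuals not reversing it. H1a belongs to Aim 1 and is not among the primary or secondary outcomes in C7, so the primary comparison of CPAP with control is unaffected. The change is still worth making, because it is cheap and cannot be made after the data are collected.

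**What to change.** In C3, state that the study visit 2 Pediatric Sleep Questionnaire is completed before the sleep study. It can be sent with the one-week sleep log at the pre-study call, since C5 already allows email or web delivery, or be completed on arrival before lights-out. Record the completion time, and state in C8 that H1a uses the score completed before the study.

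The cost is about one line in C3 and in the operations manual, plus the C8 statement, with no new form, visit or staff. The downside is that a few families will complete the form on arrival instead of at home. The same order at study visit 4 is optional for consistency and is not needed for H1a.

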**Behavioral Assessments:** Standardized rating scales to be completed by a child's parent or guardian will include the Conners' Parent Rating Scales (CPRS-R:L) and the Child Behavior Checklist (CBCL), with the primary study outcome measure, Behavioral Index, being constructed from the sum of the T-scores from the Conners' ADHD Index and CBCL Attention Deficit/Hyperactivity Problems. Parents also will complete the CPRS-R:L and CBCL at the pre-operative meeting after signing the consent materials with their child. Although not representing a primary outcome point for this study, this assessment will serve to familiarize parents with the process of observational reporting on their child; provide important information or grouping variables for secondary analyses; and help to confirm that CPAP and control groups have equivalent behavior at baseline. Because of the importance consistently reported for the measurement of executive functioning in children with SDB, the Behavior Rating Inventory of Executive Functioning (BRIEF) also will be completed. Finally, quality of life will be measured from both the Peds-QL parent and child forms. The CPRS-R:L, CBCL, and BRIEF are available in teacher forms that will allow secondary, corroborative assessment in both a home and school environment, and help address any evident parental bias. Through experience in our laboratory and work with the multicenter Childhood Adenotonsillectomy (CHAT) trial, for which our center directs quality assurance and monitoring of behavioral and cognitive assessments, we have developed techniques to sustain strong return rates for teacher ratings.

Any or all survey instruments used in this study may be administered as paper forms or electronic versions, which may be delivered by email or via a web-based software system such as Qualtrics, or as a combination of paper and pencil and electronic formats, depending on the form type and the reporter (child, parent or teacher). *Any instrument for survey over the internet will be or is being developed through the auspices of the computer*

*support group in Psychiatry and MCIT to be sure it is HIPPA compliant, as are current measures employed in Psychiatry for their patient metrics.*

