### **(c) Exploratory Outcome Measures:**

Measures of academic achievement, fluid cognition, and REREC are all considered exploratory.

C8. Analyses. For Hypothesis 1a, post-AT SDB as an outcome variable will be defined as a respiratory disturbance index (RDI)  $\geq 1$  obstructive or mixed apnea, hypopnea, or respiratory effort-related arousal per hour of sleep. The 22-item SDB scale score (on a continuous scale from 0.0 to 1.0^43) will provide the main explanatory variable. Logistic regression models will be assessed for sensitivity to potential covariates or confounds, including age, gender, race, body mass index z-score, and socioeconomic status. Secondary analyses will focus on RDI as a continuous outcome; validated snoring, sleepiness, and behavior subscales within the SDB scale; habitual snoring as a single, previously informative question-item; and most importantly SDB data generated by innovative algorithms, as described above, exploratory analyses for RCREC, esophageal pressures, and sleep dynamics. For Hypothesis 1b, multiple linear regression models will be constructed to assess cross-sectional associations between each neurobehavioral morbidity (the Behavioral Index being the primary outcome) and the SDB questionnaire score or RDI as the main explanatory variable. Models of the SDB questionnaire will use a slightly shortened, 16-item version (as previously) to exclude behavioral questions that would correlate with outcome measures for artificial reasons. Covariates as above will be taken into account. Secondary analyses will 1) assess the impact of SDB scores or RDI on other behavioral and cognitive measures; 2) take IQ and achievement into account within the main models; and 3) test the 3 newer, computed SDB measures in place of RDI. To assess Hypothesis 2a, the investigators will define adequate adherence as at least 4 hours of electronically recorded CPAP use per night, on average over the most recent 3 months on treatment. A series of multiple linear regression models will be used, with post-CPAP improvement in neurobehavioral variables as outcomes. The pre-CPAP SDB questionnaire scores or RDI will serve as the main explanatory variables. Secondary analyses will use the 3 SDB measures generated by computer algorithms as the explanatory variables. To assess Hypothesis 2b, the same outcomes will be regressed on CPAP adherent vs. non-adherent categorization, as well as (secondarily) a continuous measure of adherence as defined by mean hours of nightly use during the last 3 months of the trial. As with Hypotheses 1a and 1b, models for 2a and 2b also will be assessed after adjustment for similar potential covariates or confounds. To assess Hypothesis 2c, intent-to-treat analyses will use models that regress each primary neurobehavioral outcome on initial CPAP vs. control group assignment, after adjustment for BMI z-scores, age,

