Contact will be made with subjects before AT (as opposed to 4 months later) for two reasons. First, the investigators would like to minimize decisions not to participate simply because good improvement in symptoms are seen after AT. Although every family will have the right to withdraw at any time from the research, the investigators believe that even children who improve after AT may well improve further with definitive treatment for any residual SDB. Second, the visit just before AT will allow the investigators to administer simple but important questionnaires that will assess SDB symptoms and neurobehavioral morbidity at baseline, before any major intervention in most cases. This could provide important opportunities to explore selection bias at study entry; adjust statistical models for SDB or neurobehavioral problem severity at entry; compare gains from AT to those from subsequent PAP; and perhaps gain insight into what symptoms prior to AT may predict ultimate need for post-surgical PAP that provides additional benefit. Further, this visit will include a very brief cognitive assessment that will give young children experience with a one-on-one testing experience to reduce subsequent novelty and improve reliability. However, an addendum to this protocol also allows enrollment after the child's adenotonsillectomy (at or before study visit 2) for families who are not able to schedule a preoperative study visit due to time constraints at the time of the initial referral, or because they were referred only after the surgery. This will allow more opportunities for participation of eligible children who would otherwise have enrolled preoperatively.

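### Aim 1 claims a risk factor for persistent morbidity, but every H1b model is cross-sectional and none uses the pre-operative Behavioral Index ratings the trial collects

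*Combined protocol and SAP*

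**What the plan says.** Section 2.2 words H1b as an association: after AT, "residual problems with behavior, cognition, and sleepiness will show associations with persistent SDB as identified by the SDB scale or polysomnography". The Impact paragraph that follows goes further. It expects the questionnaire to identify residual SDB, "which in turn is a risk factor for persistent neurobehavioral morbidity".

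Section C8 gives the test: "multiple linear regression models will be constructed to assess cross-sectional associations between each neurobehavioral morbidity" and either the SDB questionnaire score or RDI, with "the Behavioral Index being the primary outcome". The covariates are those listed for H1a, "including age, gender, race, body mass index z-score, and socioeconomic status", carried over by the sentence "Covariates as above will be taken into account". Secondary H1b analyses turn to other outcomes, add IQ and achievement, or substitute the computed SDB measures for RDI. None contains a score from before surgery.

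That score is available for many children. The Behavioral Index sums two T-scores, one from the Conners' scale and one from the CBCL, and section C5 states: "Parents also will complete the CPRS-R:L and CBCL at the pre-operative meeting". C5 assigns these ratings to secondary analyses and to a check of group balance, without naming a model. Section 6.1.a says the pre-operative visit could offer a chance to "adjust statistical models for SDB or neurobehavioral problem severity at entry". C8 does not take this up. Section C3 and section 6.1.a also allow enrolment after AT, and those children have no pre-operative rating.

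**The concern.** To say that morbidity persisted, one must know it was there before. A single SV2 score cannot separate a child whose problems failed to resolve alongside residual SDB from a child who was always more hyperactive and whose SDB was also more likely to remain. Both produce the same cross-sectional association.

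The documents make some link between pre-operative behaviour and residual SDB plausible. Section A1 reports consistent associations between SDB symptoms and behaviour, section C10.2 says the SDB scale predicted hyperactive behaviour in children having AT, and ADHD is not an exclusion. If the enrichment rule in C2 is triggered, every second child might need a high SDB score both before AT and at 4 months. The 22-item scale includes behavioural signs, so that selection could itself tie early behaviour to SV2 SDB.

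At stake is what Aim 1 may conclude, and the Impact paragraph intends that conclusion to guide evaluation after surgery. Because C8 does not commit to adjustment, whether to adjust would be decided after the data are seen.

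**Working it through.** **Inputs from the documents.** Section C9: n = 120, alpha 0.05 (taken as two-sided), detectable correlation 0.25 with 80% power, stated for H1a and extended to H1b.

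**Assumed inputs.** The documents give neither *b*, the correlation of the pre-operative with the SV2 Behavioral Index, nor *a*, the correlation of the pre-operative index with the SV2 SDB measure. I take *b* = 0.6 to 0.7 and *a* = 0 to 0.35.

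**Step 1: the plan's own figure.** Power = Φ(atanh(ρ)·√(n−3) − 1.96). With ρ = 0.25 and n = 120: 0.2554 × 10.817 − 1.96 = 0.803, and Φ(0.803) = 0.789. The stated 80% is reproduced to within about a point and is not in dispute.

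**Step 2: the planned model when residual SDB has no effect given pre-operative behaviour.** The expected correlation is *a·b*. Putting it into the Step 1 formula, with the small opposite tail added, gives the chance of a significant result:

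| *a* | *b* = 0.6: r, rejection | *b* = 0.7: r, rejection |
|---|---|---|
| 0 | 0, 5% | 0, 5% |
| 0.1 | 0.06, 10% | 0.07, 12% |
| 0.2 | 0.12, 26% | 0.14, 33% |
| 0.3 | 0.18, 50% | 0.21, 64% |
| 0.35 | 0.21, 64% | 0.245, 77% |

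At the top of the range the spurious correlation is about the 0.25 the trial is powered to find.

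**Step 3: the same setting with the pre-operative index in the model.** Simulated rejection at n = 120 is about 5% throughout, if the rating measures the confounder without error. With an assumed reliability of 0.8, *b* = 0.7 and *a* = 0.3 to 0.35, it is about 9% to 12%.

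**Step 4: a setting where adjustment misleads.** Suppose pre-operative behaviour is partly caused by pre-operative SDB (effect 0.3), residual SDB correlates 0.7 with pre-operative SDB, a stable trait links early and later behaviour, and residual SDB has a true effect of 0.25. Then *a* = 0.7 × 0.3 = 0.21; set *b* = 0.70.

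- Adjusted coefficient = (0.25 − 0.70 × 0.21)/(1 − 0.21²) = 0.103/0.956 = 0.11.
- Partial correlation = 0.103/√[(1 − 0.49)(1 − 0.0441)] = 0.103/0.698 = 0.148.
- Power = Φ(atanh(0.148)·√116 − 1.96), about 0.36, against about 0.79 unadjusted.

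These values of *a* and *b* lie inside the range of Step 2, so the correlations alone cannot tell the two settings apart.

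**Step 5: precision.** If *a* = 0, *b* = 0.65 and the true coefficient is 0.25, simulated power rises from 80% to 96% with adjustment at n = 120. That gain belongs to the case with no bias to remove and should not be added to Step 3.

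**The case against.** The strongest reply is that the plan claims little. H1b and C8 speak only of association, a risk factor need not be a cause, section 2.2 reserves causal language for the randomised Aim 2, and section A7 leaves proof to a later multicenter trial. H1b is not among the primary or the 19 secondary outcomes in C7. C8 drops the behavioural items from the SDB scale for H1b, which removes one artificial route to an association. For RDI the correlation *a* may be small: section A3 reports that several large studies found no linear dose-response between polysomnographic SDB and parent-rated outcomes. At *a* = 0 to 0.1 the false-positive rate is only 5% to 12%.

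Most of this stands, and it limits the point. A reader might infer that the trial will report long-standing behaviour as an effect of residual SDB. The documents do not support that: the bias depends on a correlation they do not give, and H1b asserts no effect. A reader might also infer that the adjusted model should replace the planned one. Step 4 shows why it should not: on the protocol's own premise that SDB harms behaviour, adjustment can remove part of a true effect.

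What the reply does not answer is the persistence wording, which no single-visit model can support, and the lack of any commitment in C8 to use a rating already collected.

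**Conclusion.** The point holds as a gap between the Aim 1 Impact wording and the H1b analysis. The possible distortion ranges from none to a spurious correlation of about 0.25, with rejection from about 5% to 77% at n = 120. That range rests wholly on the assumed correlations, and on residual SDB having no effect given pre-operative behaviour. It is likely to be nearer the low end for RDI than for the questionnaire score. The plan's power figure for H1b is sound. Neither the cross-sectional nor the adjusted model settles the question alone, but agreement between them would support a statement about persistence better than either does. The primary randomised comparison (H2c) is not affected. This is a cheap improvement worth making, not a flaw in the trial's main result.

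**What to change.** In C8, under Hypothesis 1b:

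- Keep the cross-sectional model as planned.
- Pre-specify a second model of the SV2 Behavioral Index, in children enrolled before AT, with the same covariates plus the pre-operative Behavioral Index and an indicator for chronic stimulant use. The indicator is needed because C2 specifies drug holidays only before the 4- and 10-month evaluations, so the pre-operative rating may have been made on medication.
- Report the two models side by side, with the number of children in each.
- Describe residual SDB as a risk factor for persistent behavioural morbidity only if the association also holds in the adjusted model. Otherwise state a cross-sectional association at 4 months. Use that wording in any case for cognition and MSLT sleepiness, which have no comparable pre-operative measure.
- State two limits: children enrolled after AT lack the rating and appear only in the cross-sectional model, and the adjusted model can understate a true effect if pre-operative behaviour was itself caused by SDB.

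The cost is a few sentences in the plan and one more model on data already collected. The adjusted sample will be smaller by the number enrolled after AT, which the documents do not give. As an illustration, with 90 children rated before AT, *a* = 0, *b* = 0.65 and a true coefficient of 0.25, the partial correlation is 0.25/√(1 − 0.65²) = 0.329 and adjusted power is Φ(atanh(0.329)·√86 − 1.96), about 0.89.
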